4.1. Treatment Group Presentation by Analysis

For analyses of disposition, demographics, baseline characteristics, concomitant medications, and medical history, subjects will be analyzed under their first actual treatment received (8 mg BID or 12 mg BID) in CP543.5002. The following treatment columns will be used:

- CTP-543 8 mg BID
- CTP-543 12 mg BID
- Total CTP-543

Summary tables for the laboratory evaluations, vital signs, and ECGs will include the following treatment columns referring to the starting dose in CP543.5002 and modified dose, if applicable (CP543.5002 initial treatment to CP543.5002 modified treatment):

- CTP-543 8 mg BID
- CTP-543 12 mg BID
- CTP-543 8 mg BID to CTP-543 12 mg BID
- CTP-543 12 mg BID to CTP-543 8 mg BID
- Total CTP-543

For analyses of laboratory evaluations, vital signs, and ECGs, the treatment groups CTP-543 8 mg BID and CTP-543 12 mg BID refer to subjects who initially received CTP-543 8 mg BID or CTP-543 12 mg BID, respectively, during CP543.5002 and received no qualifying dose changes. For clarity, for purposes of identifying treatment groups for these analyses, the initial dose will be the first dose that was dispensed for at least 2 visits; if no dose meets that criteria, then the initial dose is the first dose actually received in CP543.5002. A qualifying dose change is any dose change from the initial dose that spans more than one planned visit in CP543.5002 (i.e., the altered dose was dispensed at two or more consecutive visits). The treatment group CTP-543 8 mg BID to CTP-543 12 mg BID refers to subjects who received a qualifying dose change from 8 mg BID to 12 mg BID during CP543.5002. In the event of more than one qualifying dose change, only the first qualifying dose change will be considered. The treatment group CTP-543 12 mg BID to CTP-543 8 mg BID is defined similarly for qualifying dose changes from 12 mg BID to 8 mg BID.

If there are no subjects with dose adjustments meeting the criteria defined above, the CTP-543 8 mg BID to CTP-543 12 mg BID and CTP-543 12 mg BID to CTP-543 8 mg BID columns may be excluded from summaries which utilize the Safety population.

For analyses of efficacy, subjects will be classified in the same treatment groups as above for laboratory evaluations, vital signs and ECGs:

- CTP-543 8 mg BID

Sun Pharmaceutical Industries, Inc.
Statistical Analysis Plan – CP543.5002

- CTP-543 12 mg BID
- CTP-543 8 mg BID to CTP-543 12 mg BID
- CTP-543 12 mg BID to CTP-543 8 mg BID
- Total CTP-543

Subjects will further be categorized into “analysis cohorts” based on their prior treatment in the qualifying study (CTP-543 8 mg BID, CTP-543 12 mg BID, or Placebo). Unless otherwise specified in this SAP, efficacy tables will be presented separately by analysis cohort and overall, with treatment groups as columns. If <5 subjects fall under a treatment group for a given analysis cohort, that column will be dropped. All subjects will still be included in the overall column.

Summary tables for exposure, and AEs will include the following treatment columns:

- CTP-543 8 mg BID
- CTP-543 12 mg BID
- Total CTP-543

For analyses of exposure, a subject with a qualifying dose change will be treated as if the subject changed dose from one study to another and will be included under more than one treatment column. For analyses of AEs, AEs will be considered treatment-emergent with respect to the most recent dose taken prior to the start of the adverse event. Subjects may be included in more than one treatment column due to dose changes.

Mock tables and data listings will be provided as attachments to this analysis plan. Minor changes to the mocks after formal SAP approval will not necessitate re-approval unless changes to the text of the SAP are required.

All statistical deliverables will be produced, validated, and reviewed for accuracy/consistency in accordance with [REDACTED] standard operating procedures and the processes described in the statistical validation plan.

SAS® (SAS Institute, Cary, North Carolina) statistical software, version 9.4 or later, will be used for all analyses. Adverse Events and Medical History will be coded in Medical Dictionary for Regulatory Activities (MedDRA) Version 23.1. Concomitant medications will be coded in World Health Organization (WHO) Drug Global Version 2020-SEP and Anatomical-Therapeutic-Chemical (ATC) classification and preferred term.

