Pregnancy testing will be performed every 4-weeks throughout study enrollment. As in-clinic visits are performed bi-monthly following Visit 4 (Week 12), subjects will perform in-home urine pregnancy tests at Week 16, Week 24, Week 32, Week 40 AND Week 48 and 4-weeks post the final study visit. The test date and result will be documented.

In-home pregnancy testing window is  $\pm$  3 days

Collected pre-dose, when possible.

Includes fasted hematology, serum chemistry, SARS-CoV-2 testing, and lipids performed by the central lab.

At the Week 52 visit, patients will be assessed via SALT for treatment success (Responder) defined as having an absolute SALT score of  $\leq 20$  at Week 52. These responders will be eligible to continue in the OLE extension for up to a maximum of one additional year.

Study drug dispensation will occur at Visit 9 (Week 52) for RESPONDERS ONLY (defined as having a SALT score  $\leq 20$ ).

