Following reports of thrombosis with 12 mg BID after long-term administration of CTP-543 and discussions with the US Food and Drug Administration (FDA), the 12 mg BID dose was immediately discontinued and communicated under an Urgent Safety Measure. Due to implementation of this urgent safety measure, all patients previously assigned to the 12 mg BID dose will be dose reduced to the 8 mg BID dose, should they elect to continue in the trial, for the duration of the trial up to a total of 52 weeks for non-responders or a maximum of 108 weeks for responders.

At the Week 52 visit, subjects will be assessed for treatment success (Responders) defined as subjects having an absolute SALT score of ≤ 20 . These Responders will continue in the OLE extension for an additional 52 weeks. Non-responders will complete the study at Week 52. Additionally, subjects should be withdrawn from the study if in the Investigator's opinion

Sun Pharmaceutical Industries, Inc.
Statistical Analysis Plan – CP543.5002

continued study participation is undesirable or the risk-benefit profile has become unfavorable. Additional withdrawal criteria can be found in Section 7.3 of the protocol.

Subject safety will be monitored throughout the study. During the first 12 weeks, hematology, serum chemistry, and lipids will be conducted under fasted conditions every 4 weeks. Following 12 weeks on treatment, subjects will return to the clinic every 8 weeks for safety assessments until the completion of the study or until withdrawal from the study. At each study visit, an assessment should also be undertaken for any changes in the physical exam, or symptoms such as pain, swelling or tenderness in leg(s), persistent breathing difficulties or shortness of breath, or severe headache, that are suggestive of an increased risk of thromboembolism. Patients must be withdrawn if they have a prior history of thrombotic event(s) or experience a thromboembolic event.

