4.2. Assessment Time Windows

The visit schedule for all study assessments is provided in Appendix 14.1.

Sun Pharmaceutical Industries, Inc.
 Statistical Analysis Plan – CP543.5002

For scheduled visits, there will be no reassignment of the analysis visit based on date, and all scheduled visit data will appear in summary tables based on the nominal timepoint as recorded in the electronic case report form (eCRF).

Unscheduled visits and early termination visits will be reassigned based on the analysis windows in [Table 2](#) and the schedule of events. Assessments may only be re-assigned to visits where they were to be collected per the schedule of events. Unless otherwise specified, early termination visit and unscheduled visit data will be included in tables and figures if no scheduled visit data is available for the nominal eCRF recorded visit. If more than one unscheduled assessment (early termination or unscheduled) is performed within an analysis window, the assessment performed closest to the target day will be used. If more than one assessment is equally close to the target day, the latest assessment in a window will be selected as the visit used in summaries. All visits will be included in by-subject data listings.

Table 2: Analysis Windows for Unscheduled and Early Termination Visits

Nominal Visit	Safety Analyses			Efficacy Analyses		
	Lower	Target	Upper	Lower	Target	Upper
Visit 1-Baseline	1	1	1	1	1	1
Visit 2-Week 4	2	29	43	22	29	36
Visit 3-Week 8	44	57	71	50	57	64
Visit 4-Week 12	72	85	113	78	85	92
Visit 5-Week 20	114	141	169	127	141	155
Visit 6-Week 28	170	197	225	183	197	211
Visit 7-Week 36	226	253	281	239	253	267
Visit 8-Week 44	282	309	337	295	309	323
Visit 9-Week 52	338	365	393	351	365	379 ^[1]
Visit 10-Week 60	394	421	449	407	421	435
Visit 11-Week 68	450	477	505	463	477	491
Visit 12-Week 76	506	533	561	519	533	547
Visit 13-Week 84	562	589	617	575	589	603
Visit 14-Week 92	618	645	673	631	645	659
Visit 15-Week 100	674	701	729	687	701	715
Visit 16-Week 108	730	757	785	743	757	760

[1] For efficacy analyses, the upper bound at Week 52 will be 368 for non-responders and any subjects who respond but discontinue the study at the Week 52 visit, and 379 for responders who continue the study past Week 52. Subjects will be classified as responders or non-responders at Week 52 based on their Week 52 SALT assessment.

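### SAP 4.1 files each 12 mg starter's whole by-visit record according to whether a dose change came later, so the two 12 mg columns are sorted on post-baseline events

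*SAP*

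**What the plan says.** SAP 4.1 uses three schemes.

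- **Disposition, baseline and similar tables:** "subjects will be analyzed under their first actual treatment received (8 mg BID or 12 mg BID) in CP543.5002".
- **Adverse events and exposure:** an event goes to the most recent dose before onset, and exposure is divided at a qualifying change.
- **By-visit laboratory, vital-sign and ECG tables:** one column per subject for the whole study. Of the columns, '8 mg BID' and '12 mg BID' are the single-dose ones; they "refer to subjects who initially received CTP-543 8 mg BID or CTP-543 12 mg BID, respectively, during CP543.5002 and received no qualifying dose changes"; patients with a change go to a sequence column such as '12 mg to 8 mg'. SALT follows suit: "For analyses of efficacy, subjects will be classified in the same treatment groups as above for laboratory evaluations, vital signs and ECGs".

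The trigger is defined thus: "A qualifying dose change is any dose change from the initial dose that spans more than one planned visit in CP543.5002", that is, the altered dose dispensed at two or more consecutive visits. Under SAP 4.2, "all scheduled visit data will appear in summary tables based on the nominal timepoint". Within a prior-treatment cohort, "If <5 subjects fall under a treatment group for a given analysis cohort, that column will be dropped".

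Two other rules decide who has a change. SAP 3 reports what the urgent safety measure meant for dosing: "all patients previously assigned to the 12 mg BID dose will be dose reduced to the 8 mg BID dose, should they elect to continue". SAP 8.2.3.1 places these reductions on or after 28 April 2023. Protocol Table 1 (repeated in SAP 14.1) adds: "Study drug dispensation will occur at Visit 9 (Week 52) for RESPONDERS ONLY". Protocol 4.2 ties the discontinuation of Week-52 non-responders to Section 8.1.1, which describes an EMA decision of January 2023. Neither document says from when that rule, or the extension for responders, applied.

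**The concern.** A Week 4 SALT score is placed in a column by something that may happen more than a year later. That is harmless if dose changes are rare and unrelated to outcome. Here the safety measure changed the dose of every 12 mg patient who continued, and continuing past Week 52 depends on SALT at Week 52. Patients with two 8 mg dispensings then tend to be responders. Those left in '12 mg BID' tend to be non-responders, dropouts and those who declined to continue.

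At stake are the by-visit tables of the only efficacy endpoint (SAP 8.2.2 and 8.2.3). The prior-placebo cohort is the most exposed. It holds the only patients randomised between doses (SAP 7.2). Its 8 mg column stays nearly intact, it has no intact 12 mg column, and its Total mixes the doses.

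**Working it through.** The plan gives no sample size or power, so there is no figure of its own to reproduce. The check is date arithmetic followed by an illustration.

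**1. Dates.** Inputs: first patient September 2021 and last completion July 2024 (Protocol 1, both estimates); Week 108 = Day 757 (SAP Table 2); measure on 28 April 2023 (SAP 8.2.3.1).

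- 1 Sep 2021 to 28 Apr 2023 = 604 days = 86.3 weeks. This is below 108, so no continuing patient had finished.
- Latest entry: 31 Jul 2024 − 756 days = 6 Jul 2022. That patient was at Week 42.3 on 28 Apr 2023, so all Week 4–36 visits precede the measure. Apart from discretionary changes (SAP 7.2), both 12 mg columns hold only 12 mg values there.
- Week 52 reached before the measure: entry by 29 Apr 2022. With uniform entry (assumed), 240/308 = 78%.

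**2. Mixing of doses within '12 mg to 8 mg'.** Share of visits at week w that fall after the measure = 1 − (604 − 7w)/308:

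- Week 52: 1 − 240/308 = 22%
- Week 60: 1 − 184/308 = 40%
- Week 68: 1 − 128/308 = 58%
- Week 76: 1 − 72/308 = 77%
- Week 84: 1 − 16/308 = 95%

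For ECG, mixing concerns only Week 52 and early-termination values (SAP 9.6.3.1).

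**3. Displayed Week-52 response (SALT ≤ 20).** Let p be the true rate among 12 mg starters with a Week-52 score, f the fraction of responders who stay in '12 mg BID', and g the same fraction for non-responders.

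'12 mg BID' shows p·f / [p·f + (1−p)·g].

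f and g come from simulating 400,000 12 mg starters per case. Assumptions not in the documents: uniform entry; 15% dropout before and 10% after Week 52; 0–20% declining at the measure; all switches on 28 Apr 2023; planned dispensing only; no discretionary changes.

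- **A.** Rule and extension applied throughout: f = 0.044–0.199, g = 1.
- **B.** No responder past Week 52 before the measure was offered the extension: f = 0.781–0.817, g = 1.
- **C.** All non-responders past Week 52 before the measure stayed on: f = 0.044–0.199, g = 0.262–0.382.

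Example, case A, p = 0.35, nobody declining: 0.0154/(0.0154 + 0.65) = 2.3%.

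| Case | '12 mg BID' at true 35% | at 50% | at 65% | '12 mg to 8 mg' |
|---|---|---|---|---|
| A | 2.3–9.7% | 4.2–16.6% | 7.6–27.0% | 100% |
| B | 29.6–30.6% | 43.9–45.0% | 59.2–60.3% | 100% |
| C | 8.3–21.9% | 14.4–34.3% | 23.8–49.2% | 41%, 56%, 71% |

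Another run of case C at 35% put the lower end at 9%. Spreading the switches over 8 weeks changes case A at 35% only to 2–11%. Discretionary reductions in 5–10% of patients bring '12 mg to 8 mg' down to 80–94% at 35%. In every case the two columns lie on either side of the true rate.

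**4. Denominator.** SAP 4 uses the header N unless stated otherwise. Per 100 starters in case A at 35%, nobody declining: 85 are scored and 0.35 × 85 = 29.75 respond, of whom 0.044 × 29.75 = 1.31 stay in '12 mg BID'. That column holds 100 − 28.44 = 71.56 patients, so it shows 1.31/71.56 = 1.8%; with 20% declining, about 7%. The pooled rate is then just under 30%, or about a point lower with 20% declining, not 35%.

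**5. Prior-placebo cohort.** The parent trials' Week-24 rates (Protocol 4.2) serve only as assumed Week-52 rates, among scored patients.

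| True 8 mg vs 12 mg | A: '12 mg BID' | B | C |
|---|---|---|---|
| 29.6% vs 41.5% | 3.0–12.4% | 35.7–36.7% | 10.6–27.0% |
| 33.0% vs 38.3% | 2.7–11.0% | 32.7–33.7% | 9.4–24.4% |

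Against the nearly intact 8 mg column, the dose order is reversed in A and C. In B it is kept for the first pair and all but erased for the second.

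**The case against.** The strongest objection is that the size rests on an undated rule. If the extension itself came late (case B), '12 mg BID' sits only about 4 to 6 points below the truth. That stands, and it rules out a single headline figure.

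Other points also stand:

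- The study is descriptive, with no between-dose test.
- Column definitions are explicit and by-subject listings are planned.
- Counts, means and SDs can be pooled across the two 12 mg columns; medians cannot, nor can a column dropped for having fewer than five subjects.
- Total columns and the adverse-event and exposure tables are not affected in this way.
- SAP 8.2.3.1 plots SALT change by visits since reduction, and its redacted part may hold more. Its visible text does not cover the by-visit columns before reduction, or laboratory and vital-sign data.

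Three stronger readings are tempting but unsupported. A reader might infer that the tables will show 12 mg doing worse than 8 mg; case B shows that this need not happen. A reader might infer biased laboratory or vital-sign results; the sorting applies to those tables, but nothing in the documents links SALT response to those values and no bias has been quantified. A reader might infer that the submission's interim analysis is affected; its data freeze was planned for late 2022 (SAP 8.1.2), before the forced reductions.

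**Conclusion.** The structural point follows from the text. SAP 4.1 sorts whole by-visit records on a later event, whereas the SAP's disposition, adverse-event and exposure tables avoid this. On the estimated study dates, a difference between the two 12 mg columns at Weeks 4–36 reflects that sorting, and from about Week 52 '12 mg to 8 mg' mixes values taken on both doses. The direction at Week 52 was the same in every case examined. The size is not determinable: for a true 35%, '12 mg BID' may show anything from about 2% to 31%, on assumed entry, dropout and decline rates and depending on when the rule and extension began. It would go too far to say that the columns separate responders from non-responders outright; that holds nearly only in case A. This is a worthwhile improvement to the presentation, and no planned inference is invalidated.

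**What to change.** 1. Make the first dose received in CP543.5002, already defined in SAP 4.1 for disposition, the main column for by-visit SALT, laboratory, vital-sign and ECG tables.
2. For 12 mg starters, tabulate visits before and after each patient's own safety-measure reduction separately, so that values from after that reduction are not shown as 12 mg.
3. Keep the dose-sequence columns as a supplementary display, with a footnote that membership depends on later events.
4. State in the SAP from when the Week-52 rule and the responder extension applied, and footnote that visits after Week 52 include responders only where the rule applied.

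The cost is SAP wording and programming; no new data are needed. The downsides are extra tables, fewer 12 mg patients at later visits and some mixing from discretionary changes. The before/after split does not remove the selection of responders after Week 52, which is why the footnote is needed.

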4. GENERAL ANALYSIS AND REPORTING CONVENTIONS

The following is a list of general analysis and reporting conventions to be applied to this study, unless otherwise specified. Departures from these general policies will be described, if applicable, in the appropriate sections of this SAP. When this situation occurs, the rules set forth in the specific section take precedence over the general policies.

All data displays (tables, listings, and figures) will have a header showing the sponsor company name, protocol number, and page number, as well as a footer indicating file name, run date/time, and display status (i.e. “DRAFT” or “FINAL”). Unless otherwise noted, summary tables and data listings will be summarized by treatment group CTP-543 8 mg BID, CTP-543 12 mg BID, and Total CTP-543. All data for analysis will be listed by-subject and by CTP-543 8 mg or 12 mg BID.

Categorical variables will be summarized using counts (n) and percentages (%) and will be presented in the form “n (xx.x)”, with percentages rounded to one decimal place. If a count is 0, no percentage will be shown. If a percentage is 100%, 100.0 will be shown. To ensure completeness, summaries for categorical variables will include all categories, even if no subjects had a response in a particular category. Unless otherwise specified, the denominator for each percentage will be based on the number of subjects in the population being summarized (i.e. header N).

Continuous variables will be summarized using mean, standard deviation (SD), minimum, maximum, median, and number of subjects. The mean and median will be reported to an additional level of precision than the original observations, and the standard deviation will be reported to two additional levels of precision than the original observations. The minimum and maximum will be the same precision as the original collected data. The precision for some original collected data and derived variables are longer than required for clinical interpretation (e.g., >15 decimals). In these situations, the number of decimal places will be determined by the table of precision that will be included with the table shells.

Summary tables and data listings:

- No preliminary rounding will be performed; rounding will only occur after analysis.

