9.2. Extent of Exposure

Study drug exposure will be summarized for the CTP-543 8 mg BID and CTP-543 12 mg BID treatment groups and overall. Duration of exposure in weeks will be calculated as (date of last dose of study drug minus the date of first dose of study drug + 1 day)/7. Study drug exposure will be summarized categorically by duration of treatment in weeks ($\geq 4, \geq 8, \geq 12, \geq 16, \geq 20, \geq 24, \geq 28, \geq 36, \geq 44, \geq 52, \geq 60, \geq 68, \geq 76, \geq 84, \geq 92, \geq 100$, and ≥ 108) and will include a summary of subjects receiving ≥ 1 dose. Dose interruptions, missed doses, and partial doses will be ignored. Subjects who are lost to follow-up and were on treatment as of their last visit will be counted as receiving their last dose on the date of the last visit completed. Duration of study drug exposure in weeks as a continuous variable will also be summarized.

All summaries of exposure will be limited to exposure in CP543.5002.

Duration of cumulative study drug exposure in weeks for subjects who entered the OLE will be calculated as (OLE treatment end date – OLE treatment start date – the number of days of missed dose + 1)/7. Duration of cumulative study drug exposure will be summarized and calculated in the same manner as study drug exposure, except that any period of dose interruptions or missed doses will be subtracted. If the reason not dosed is “dose interruption”, it will be counted as a missed dose regardless of the actual number of tablets taken. If the reason not dosed is “missed dose” or “partial dose” and no tablets were taken, it will be treated as a missed dose; if the reason not dosed is “missed dose” but 1 tablet was taken, it will be treated as a partial dose.

Duration of exposure up to a qualifying dose change in CP543.5002 will be summarized as a categorical measure based on treatment sequence between the qualifying study and initial dosing in CP543.5002, as follows: Placebo to 8 mg BID, Placebo to 12 mg BID, 8 mg BID to 8 mg BID, and 12 mg BID to 12 mg BID. Duration of exposure up to a qualifying dose change for subjects previously on placebo will be separately tabulated from that of subjects previously on active drug in the qualifying study. For purposes of these tabulations, if a subject experiences a qualifying dose change, duration of exposure will be counted up to the qualifying dose change. Dose interruptions, missed doses, and partial doses will be ignored.

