Duration of exposure after a qualifying dose change in the OLE study will be summarized as a categorical measure based on treatment sequence for subjects with any qualifying dose change in CP543.5002. The following treatment sequences will be used (based on treatment sequence within CP543.5002): 12 mg BID to 8 mg BID and 8 mg BID to 12 mg BID. For purposes of this tabulation, the relevant duration of exposure will be the last dose of study drug in CP543.5002 minus the date of the first qualifying dose change + 1 day. Therefore, if a subject experiences

more than one qualifying dose change, the subject will be classified according to the first qualifying dose change. Dose interruptions, missed doses, and partial doses will be ignored.

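### The 8 mg adverse-event column pools patients reduced from 12 mg with 8 mg starters and no person-time rate is planned, so its percentage describes neither group

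*SAP*

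**What the plan says.** **AE tables.** SAP 4.1 lists three columns: 8 mg, 12 mg and Total. Attribution is by dose at onset: "AEs will be considered treatment-emergent with respect to the most recent dose taken prior to the start of the adverse event". It adds: "Subjects may be included in more than one treatment column due to dose changes". SAP 9.3 repeats the rule and plans numbers and percentages of subjects, plus event counts. By the default in SAP 4, a percentage is taken over the column's header N. The SAP text does not say how N is formed for an AE column when a patient appears in two.

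**Who moves.** Under the urgent safety measure (SAP 3, Protocol 6.1), every continuing 12 mg patient goes to 8 mg. SAP 8.2.3.1 counts these reductions from 28 Apr 2023.

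**Other tables.** For laboratory, vital-sign, ECG and efficacy summaries, SAP 4.1 limits the 8 mg group to patients with no qualifying change and adds sequence columns: "The treatment group CTP-543 12 mg BID to CTP-543 8 mg BID is defined similarly for qualifying dose changes". On the definition: "A qualifying dose change is any dose change from the initial dose that spans more than one planned visit in CP543.5002".

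**Exposure.** Exposure tables use the same three columns as AE tables, but "a subject with a qualifying dose change will be treated as if the subject changed dose from one study to another". SAP 9.2 states: "Duration of study drug exposure in weeks as a continuous variable will also be summarized". It also tabulates exposure up to a qualifying change by sequence, and "Duration of exposure after a qualifying dose change in the OLE study will be summarized as a categorical measure based on treatment sequence".

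**Protocol.** Protocol 11.2 asks for as-treated summaries and leaves the dosing regimens to be defined in the SAP.

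**The concern.** Long-term safety is the first-named objective, and 8 mg is the only continuing dose. A reader will naturally take the 8 mg AE percentage as the experience of patients treated with 8 mg in this study. As planned, it blends two groups that differ in two ways:

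- **Follow-up.** A reduced patient brings only the time left after reduction, but may count as a full patient in N. This pulls the percentage down.
- **History.** A reduced patient has earlier 12 mg exposure in this study, and the safety measure followed thrombosis reports after long-term 12 mg use. This could push the percentage up. In the other direction, a thromboembolic event requires withdrawal, so patients reach the reduction only if they had no such event on 12 mg.

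A single percentage cannot show which effect dominates. The SAP separates these patients almost everywhere else, so AE tables are the exception.

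**Working it through.** The plan states no AE rate, sample size or accrual curve, so there is no figure of its own to reproduce. The calculation below shows what the pooling can do under stated assumptions.

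**Inputs from the documents:** treatment for 52 weeks (364 days, non-responders) or at most 108 weeks (756 days, responders); estimated first entry September 2021 and last completion July 2024 (Protocol synopsis); reduction from 28 Apr 2023.

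**Assumptions:** uniform entry from 1 Sep 2021 to 31 Mar or 30 Jun 2022 (July 2024 less 108 weeks is 6 Jun to 6 Jul 2022); equal numbers starting each dose; Week 52 responders 35% or 50% at both doses, or 35% at 8 mg and 45% at 12 mg; no dropout; all continue after reduction; constant hazard of 0.005, 0.1 or 0.3 per year.

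**Formulas:** incidence = mean of 1 - exp(-hazard x years). Column percentage = (events in 8 mg starters + events after reduction) / (8 mg starters + reduced patients in N).

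**Worked case** (entry to 30 Jun 2022, 35% responders, 0.1 per year), per 8 mg starter:

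1. 8 mg starters: 0.65 x (1 - exp(-0.1 x 364/365.25)) + 0.35 x (1 - exp(-0.1 x 756/365.25)) = 0.65 x 0.0949 + 0.35 x 0.1870 = 12.7%.
2. Entry spans 302 days, and reduction falls on day 604 from 1 Sep 2021. Non-responders are reduced only if they entered after day 240 (604 - 364), a share of 62/302, with 0-62 days left. All responders are reduced, with 152-454 days left. Reduced share of 12 mg starters: 0.65 x 62/302 + 0.35 = 0.483.
3. Events after reduction: 0.1334 x 0.0084 + 0.35 x 0.0793 = 0.0289.
4. Every reduced patient in N: (0.1271 + 0.0289)/1.483 = 10.5%, which is 17% lower than 12.7%.
5. N limited to patients with more than 56 days left (an approximation to the qualifying-change rule): reduced share 0.65 x 6/302 + 0.35 = 0.363, and 0.1560/1.363 = 11.4%, which is 10% lower.
6. Hazard doubled after reduction: events 0.1334 x 0.0168 + 0.35 x 0.1519 = 0.0554. The column is 0.1825/1.483 = 12.3% (3% lower), or 0.1825/1.363 = 13.4% (5% higher) under the 56-day N.

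**Full grid** (simulation, 400,000 patients per starting dose; 200,000 at 12 mg where 12 mg starters are halved). Mean follow-up is 1.37-1.53 years per 8 mg starter and 0.62-0.71 year after reduction. With every reduced patient in N, they form 26-38% of the column. Column percentage relative to 8 mg starters:

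| Setting | Every reduced patient in N | 56-day N |
|---|---|---|
| Equal hazards | 11-20% too low | 9-18% too low |
| Dropout 0.15/year | 9-17% too low | 6-14% too low |
| 70% continue after reduction | 8-16% too low | 7-14% too low |
| Half as many 12 mg starters | 6-13% too low | 5-11% too low |
| Last three combined | 4-8% too low | 3-6% too low |
| Post-reduction hazard x 2 | 4% too low to 1% too high | not tabulated; see step 6 |
| Post-reduction hazard x 2.5 | 2-9% too high | not tabulated |

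**Would a rate alone suffice?** Take 100 patients on 8 mg throughout, 100 reduced patients and 50 first events per 100 person-years.

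- Equal hazards, 108 weeks against 24 weeks: the column shows (64.6 + 20.6)/2 = 42.6% against 64.6%, while the rate is 50 per 100 person-years in both groups. The rate removes the follow-up effect.
- Doubled hazard after reduction, 52 weeks against 56 weeks: the column shows (39.3 + 65.9)/2 = 52.6% against 39.3%. The pooled rate is (39.3 + 65.9)/(39.3/0.5 + 65.9/1.0) = 72.8 per 100 person-years, against 50 in 8 mg patients. The rate does not remove the mixing, so a separate column is needed too.

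**Two dose-change rules.** AEs move column at any dose change, exposure only at a qualifying one. With entry to 30 Jun 2022, 15-25% of reduced patients have at most 56 days left. Any AE they have then counts under 8 mg, while their short 8 mg time is not split out in the exposure tables. They hold only 2-3% of post-reduction time, and 0.04-2.3% of them would have an event (at most 0.25 x 0.023, about 0.6% of reduced patients). With entry to 31 Mar 2022 the share is zero.

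**The case against.** The strongest reply is that this is a legitimate presentation choice. Dose-at-onset attribution is as-treated, Protocol 11.2 hands the regimen definition to the SAP, and the SAP openly says that patients may appear twice. The study is descriptive, no 12 mg versus 8 mg contrast is planned, and the Total column is unaffected by the split. Listings keep every AE visible by subject, and exposure is tabulated both up to and after a qualifying change, so a careful reader could rebuild the split.

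Most of this stands. The attribution rule is not an error and need not change. But as-treated does not require pooling, since a 12-to-8 mg column is equally as-treated and SAP 4.1 already uses one. Rebuilding the split by hand is no substitute for a table. A pooled rate taken from the exposure tables would still mix the groups and would pair AEs and time split by different rules.

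A reader might infer three stronger things that the documents do not support:

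- **That the plan makes 8 mg look safer than it is.** The 11-20% figure assumes equal hazards and so measures shorter follow-up only. It says nothing about the effect of earlier 12 mg exposure, and a hazard ratio of 2.5 reverses the sign.
- **That 15-25% of reduced patients would have 8 mg AEs with no matching exposure.** That share describes how patients are classified. Very few of them would have an event.
- **That thromboembolic events could be hidden.** They remain in the by-subject listings.

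**Conclusion.** The point holds as a gap in presentation. The SAP text pools post-reduction AEs with those of 8 mg starters, plans no person-time rate, and leaves the N of the AE columns unstated. The 8 mg percentage therefore does not describe patients on 8 mg throughout this study, and no planned AE table does.

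Direction and size cannot be fixed from the documents. Accrual, dose split, response, dropout, continuation and post-reduction hazard are all assumed. With equal hazards the column is too low by between 3-6% (the three sensitivities combined, 56-day N) and 11-20% (none of them, every reduced patient in N). With a doubled post-reduction hazard and every reduced patient in N it is close to right, and beyond that it is too high.

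The mock tables attached to the SAP and the separate integrated-safety SAP were not available. Either might already state the denominators or plan a rate. The change should be made because it is cheap and serves the first-named objective, but nothing here invalidates the analysis.

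**What to change.** - Keep the crude counts and the most-recent-dose attribution.
- In the AE tables, show events after a dose change in their own column (12-to-8 mg and, if any occur, 8-to-12 mg). The 8 mg and 12 mg columns then hold only events and time on the starting dose.
- Add exposure-adjusted incidence rates (subjects with an event per 100 person-years, 95% CI) for all TEAEs, serious TEAEs and thromboembolic events, the last defined by a prespecified MedDRA term list.
- Compute person-time from actual dose dates under the same most-recent-dose rule as the events. The qualifying-change rule of SAP 9.2 should not be used here, because it would leave AEs after a short reduction in the 12 mg column.
- State the N of each AE column in the SAP text.

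Cost: SAP wording, a few extra tables, a person-time derivation separate from SAP 9.2, and a term list. Dosing and AE dates are already collected, and nothing in patient management changes. The rates assume a roughly constant hazard, which may fit poorly for events that arise after long exposure, so the crude counts should stay beside them.
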